12.4.8 Interim Analysis

No interim analysis is planned for this study.

13 STUDY GOVERNANCE CONSIDERATIONS

13.1 Quality Control

When reviewing data collection procedures, the discussion will include identification, agreement and documentation of data items for which the eCRF will serve as the source document.

During the study, the data will be monitored to verify that:

- Data are authentic, accurate, and complete.
- Safety and rights of subjects are being protected.
- Study is conducted in accordance with the currently approved protocol and any other study agreements, GCP, and all applicable regulatory requirements.

13.2 Quality Assurance

To ensure compliance with GCP and all applicable regulatory requirements, GSK CH may conduct a quality assurance assessment and/or audit of the PPD records, and the regulatory agencies may conduct a regulatory inspection at any time during or after completion of the study.

In the event of an assessment, audit or inspection, PPD must agree to grant the advisor(s), auditor(s) and inspector(s) direct access to all relevant documents and to allocate their time to discuss the conduct of the study, any findings/relevant issues and to implement any corrective and/or preventative actions to address any findings/issues identified.

will notify GSK CH or its agents immediately of any regulatory inspection notification in relation to the study.

The GSK CH will be available to help PPD prepare for an inspection.

13.3 Regulatory and Ethical Considerations

13.3.1 Institutional Review Board/ Ethics Committee

It is the responsibility of PPD to have prospective approval of the study protocol, protocol amendments, inform consent documents, and other relevant documents, e.g. recruitment advertisements, if applicable, from the IRB/EC. All correspondence with the

Protocol Number: 216953

IRB/EC should be retained in the eTMF. Copies of IRB/EC approvals should be forwarded to GSK CH prior to the initiation of the study, and also when subsequent amendments to the protocol are made.

The only circumstance in which an amendment may be initiated prior to IRB/EC approval is where the change is necessary to eliminate apparent immediate hazards to the subjects. In that event, the investigator must notify the IRB/EC and GSK CH in writing immediately after the implementation.

13.3.2 Ethical Conduct of the Study

The study will be conducted in accordance with the protocol and legal and regulatory requirements, as well as the general principles set forth in the International Ethical Guidelines for Biomedical Research Involving Human Subjects (Council for International Organizations of Medical Sciences 2002), International Ethical Guidelines for Health-Related Research Involving Humans (Council for International Organizations of Medical Sciences, 2016), guidelines for GCP (ICH 1996 and revision 2), and the Declaration of Helsinki (World Medical Association 2013).

In addition, the study will be conducted in accordance with the protocol, the ICH guideline on GCP, and applicable local regulatory requirements and laws.

13.3.3 Subject Information and Consent

All parties will ensure protection of subject personal data and will not include subject names or other identifiable data in any reports, publications, or other disclosures, except where required by laws.

When study data are compiled for transfer to GSK CH and other authorized parties, subject names, addresses, and other identifiable data will be replaced by numerical codes based on a numbering system provided by GSK CH in order to de-identify study subjects.

will maintain a confidential list of subjects who participated in the study, linking PPD each subject's numerical code to his or her actual identity. In case of data transfer, GSK CH will maintain high standards of confidentiality and protection of subjects' personal data consistent with applicable privacy laws.

The inform eIC documents must be in compliance with ICH GCP, local regulatory requirements, and legal requirements, including applicable privacy laws.

The inform eIC documents used during the informed consent process must be reviewed and approved by the sponsor, approved by the IRB/EC before use, and available for inspection.

must ensure that each study subject, is fully informed about the nature and objectives of the study and possible risks associated with participation.

13.3.4 Subject Recruitment

Advertisements approved by IRBs/ECs may be used as recruitment procedures. Use of ethics committee approved, generic, pre-screening questionnaire to assess basic subject characteristics to determine general eligibility for this study is allowed. This pre-screening questionnaire will be accessed by subjects clicking on ads on social media, which will direct them to a landing page.

Protocol Number: 216953

GSK CH will have an opportunity to review and approve the content of any study recruitment materials directed to potential study subjects before such materials are used.

13.3.5 Reporting of Safety Issues and Serious Breaches of the Protocol or ICH GCP

Within GSK CH a serious breach is defined as a breach likely to affect to a significant degree the safety and rights of a subject or the reliability and robustness of the data generated in GSK CH-sponsored human subject research studies.

In the event of any prohibition or restriction imposed (i.e., clinical hold) by an applicable competent authority in any area of the world, or if PPD is aware of any new information that might influence the evaluation of the benefits and risks of the investigational product, GSK CH should be informed immediately.

In addition, PPD will inform GSK CH immediately of any urgent safety measures taken to protect the study subjects against any immediate hazard, and of any serious breaches of this protocol or of ICH GCP that PPD becomes aware of.

13.4 Posting of Information on Publicly Available Clinical Trial Registers

Study information from this protocol will be posted on publicly available clinical trial registers before enrollment of subjects begins in accordance with applicable GSK CH processes.

GSK intends to make anonymized subject-level data from this trial available to external researchers for scientific analyses or to conduct further research that can help advance medical science or improve patient care. This helps ensure the data provided by trial participants are used to maximum effect in the creation of knowledge and understanding

13.5 Provision of Study Results to Investigators

N/A

13.6 Records Retention

Following closure of the study, PPD must assure that the subject's anonymity will be maintained. On eCRFs or other documents submitted to GSK CH, subjects should not be identified by their names or initials, but by an identification code. PPD should keep a separate log of subjects' codes, names and addresses. Documents not for submission to GSK CH, should be maintained by PPD in strict confidence.

Records and documents, including signed eIC, pertaining to the conduct of this study must be retained by PPD as per the signed contractual agreement, from the issue of the final Clinical Study Report (CSR) or equivalent summary, unless local regulations or institutional policies require a longer retention period. The minimum retention time will meet the strictest standard applicable to that site for the study (US requirement is 30 years), as dictated by any institutional requirements or local laws or regulations, GSK CH standards/procedures, and/or institutional requirements.

No study document should be destroyed without a prior written agreement between GSK CH and PPD must notify GSK CH of any changes in the archival

Protocol Number: 216953

arrangements, including, but not limited to, transfer of ownership of the records in the event the investigator is no longer associated with the site.

13.7 Conditions for Terminating the Study

Premature termination of this study may occur because of a regulatory authority decision, change in opinion of the IRB/EC, or study product safety problems, or at the discretion of GSK CH

If a study is prematurely terminated, GSK CH will promptly notify PPD After notification, PPD must promptly contact all participating subjects and should assure appropriate follow-up for the subjects. As directed by GSK CH, all study materials must be collected and all CRF's completed to the greatest extent possible. Where required by the applicable regulatory requirements, GSK CH should inform the regulatory authority(ies) and PPD should promptly inform the IRB/EC and provide the IRB/EC a detailed written explanation of the termination or suspension.

If the IRB/EC terminates or suspends its approval/favorable opinion of a trial, PPD should promptly notify the GSK CH and provide GSK CH with a detailed written explanation of the termination or suspension.

Upon completion or premature discontinuation of the study, the GSK CH study accountable person will conduct closure activities with PPD as as appropriate, in accordance with applicable regulations including GCP, and GSK CH Standard Operating Procedures.

15 APPENDICIES

15.1 ABBREVIATIONS

The following is a list of abbreviations that may be used in the protocol.

Table 15-1 Abbreviations

Abbreviation	Term	
AE	adverse event	
ANOVA	analysis of variance	
CMG	Case Management Group	
CSR	Clinical study report	
DH	Dentin hypersensitivity	
DHEQ	Dentin hypersensitivity experience questionnaire	
EC	ethics committee	
ECG	Echocardiogram	
eCRF	Electronic Case Report Form	
EDC	Electronic Data Capture	
elCF	Electronic informed consent form	
ePRO	Patient reported outcome	
eTMF	Electronic trial master file	
GCP	Good Clinical Practice	
GSKCH	GlaxoSmithKline Consumer Healthcare	
HSI	Human subject information	
ICH	International Conference on Harmonization	
IRB	institutional review board	
K	potassium	
MedDRA	Medical dictionary for regulatory activities	

Property of GSK Consumer Healthcare - Confidential

Protocol Number: 216953

Abbreviation	Term	
MFC	Master Formulation Code	
N/A	not applicable	
NPRS	Numeric Pain Rating Scale	
NRS	Numeric Rating Scale	
OHrQoL	Oral health related quality of life	
PII	Personal Identifiable Information	
RAP	reporting and analysis plan	
RCTs	Randomized controlled trials	
RWD	Real world data	
RWE	Real world evidence	
SAE	Serious adverse event	
SUSAR	Suspected unexpected serious adverse event	
VAS	Visual analogue scale	

# **Abbreviations**

Abbreviation	Definition
ADS	Analysis Dataset
AE	Adverse Event
ANOVA	Analysis of Variance
CSR	Clinical study report
DH	Dentin hypersensitivity
DHEQ	Dentin hypersensitivity experience questionnaire
elC	Electronic Informed Consent
FCS MI	Fully Conditional Specification Multiple imputation
GSKCH	GlaxoSmithKline Consumer Healthcare
ITT	Intent To Treat
MAR	Missing At Random
MCAR	Missing Completely At Random
MedDRA	Medical dictionary for regulatory activities
mITT	Modified Intent To Treat
NPRS	Numeric Pain Rating Scale
NRS	Numeric Rating Scale
OHrQoL	Oral health related quality of life
SAE	Serious Adverse Event
SAP	Statistical Analysis Plan
SD	Standard Deviation
VAS	Visual analogue scale

PPD	GSK-001 SAP	
–	Page 6 of 14	Version 1.0
	0 01 14	1.0

### Scope

This document describes the analysis plan for the statistical analysis of the study GSK-001, study explanation.

This Statistical Analysis Plan (SAP) will provide details to further elaborate statistical methods as outlined in the study protocol and describe the analysis conventions to guide the statistical programming work.

## **Study Introduction**

### 3.1 Study Background

Dentin hypersensitivity (DH) has been defined as 'pain derived from exposed dentine in response to chemical, thermal, tactile, or osmotic stimuli which can't be explained as arising from any other dental defect or disease' (Addy et al, 1985; Canadian Advisory Board on Dentin Hypersensitivity, 2003). The hydrodynamic theory of DH hypothesizes that a stimulus external to the tooth (for example, a temperature/osmotic differential, pressure) causes movement of the fluid resident within exposed dentinal tubules (Brännström, 1963). This movement may stimulate nerve processes in the dental pulp (Addy, 2002; Hall et al, 2000), resulting in the characteristic short, sharp pain of DH.

Currently there are two approaches for the management of DH: nerve desensitization and the occlusion of exposed dentin tubules. Nerve depolarising agents, typically potassium salts, generally require a period of use (14 to 28 days) before their benefit is established. The delivery of potassium ions to the dentine-pulp junction (odontoblastic layer) via dentinal tubules is believed to result in depolarisation of the afferent nerve membrane thereby blocking the pain response. The second approach uses tubule occluding agents which physically block the exposed end of the dentinal tubules, thus reducing dentinal fluid movement and pulpal irritation. Tubule occluding agents such as strontium and stannous salts, bioglasses, silicas or oxalates serve to seal or block the dentine tubules and thereby reduce the effect of external stimuli. Such agents are believed to function by precipitating insoluble materials onto the dentine surface and/or within the dentinal tubules to reduce dentinal fluid transport.

Recently, there have been a wider consideration to the psychosocial impacts of DH on everyday life (Gibson *et al*, 2015). One qualitative study showed that DH can be triggered by several stimuli and responses, not always described as pain, can affect everyday activities such as eating, drinking, tooth brushing, talking and social interactions (Gibson *et al*, 2015).

Oral health-related quality of life (OHrQoL) questionnaires are tools increasingly used in dentistry to capture the impact of clinical interventions on OHrQoL, however these measures cover a number of oral health conditions which lead to limitations of these tools and may not detect the nuances of a specific condition (Bekes *et al*, 2009). The Dentine Hypersensitivity Experience Questionnaire (DHEQ) is a validated, condition specific measure of OHrQoL in relation to DH (Baker *et al*, 2014) (Boiko *et al*, 2010). It was developed by GSKCH in

PPD		GSK-001 SAP
1 1 0	Page 7 of 14	Version
	/ of 14	1.0

collaboration with Sheffield University through a robust theoretical framework, specific for DH (Boiko *et al*, 2010), and has shown reliability and validity in both a general population (Porritt *et al*, 2016) and in clinical studies (Boiko 2010, Gibson *et al*, 2015). The conception, development, validation, and initial usage of the DHEQ has been published (Robinson, 2014). The measure has been validated with both long- and short-form versions, comprising 48 (Baker *et al*, 2014; Boiko *et al*, 2010) and 15 (Machuca *et al*, 2014) questions respectively, and has been translated into multiple languages (e.g., Chinese, Turkish, Portuguese) confirming its global relevance (Başaran and Celik, 2018) (Douglas-De-Oliveira *et al*, 2018) (He and Wang, 2015a) (He and Wang, 2015b).

Data generated as part of GSKCH efficacy clinical studies, showed robust and positive results on the relief and management of DH in clinical measurements and OHrQoL. However, these results have been obtained from randomized controlled trials which include strict study procedures and controlled, but contrived DH stimuli. These studies may not necessarily fully reflect the general dental population when challenged with real world sensitivity stimuli.

Based on these assumptions, this will be a real-world evidence study which will include subjects among a general population who suffer from DH (self-reported symptoms). This study will aim to evaluate the impact of a recommended daily use of desensitizing toothpaste on oral health related quality of life. Data generated will give real world information on the impact of a daily use DH treatment on oral health related quality of life.

### 3.2 Study Objectives

## 3.2.1 Primary Objective

To describe subjects' oral health related quality of life over a 24-week period following the use of a sensitivity toothpaste containing 5% potassium nitrate, as measured by the DHEQ-48 in a population of DH sufferers.

## 3.2.2 Exploratory Objectives

- To explore subjects' oral health related quality of life over a 24week period following the use of a sensitivity toothpaste containing 5% potassium nitrate, as measured by the DHEQ-48 in further characterisation of DH sufferers by subgroups.
- To characterise subjects' change in oral health related quality of life over 24 weeks compared to baseline, following use of a sensitivity toothpaste containing 5% potassium nitrate, as measured by the DHEQ-48, in the overall population of DH sufferers and in 4 subgroups
- To identify the DHEQ domain items important to the overall population of DH sufferers following 24 weeks use of the sensitivity toothpaste.

PPD	GSK-001 SAP	
	Page	Version
	8 of 14	1.0

- To explore the potential impact a sensitivity toothpaste containing 5% potassium nitrate has on subjects' reported pain in relation to DH in the overall population of DH sufferers and in 4 sub-groups.
- To explore subjects' overall satisfaction with DH treatment in the overall population of DH sufferers and in 4 sub-groups.
- To describe oral hygiene habits of DH sufferers according to oral hygiene questionnaire.

### 3.3 Study Design

### 3.3.1 Study Population

Sufficient number of subjects will be screened (estimated 50% failure rate) to enroll approximately 650 subjects. This will ensure approximately 400 evaluable subjects complete the entire study (estimated 40% drop out). An enrolled subject is one who has agreed to participate in the clinical study following completion of the informed consent process directly and successfully met eligibility criteria to proceed beyond screening as applicable for the protocol design.

### 3.3.2 Study Product/Treatment

The study product is Sensodyne Fresh Mint (USA marketplace toothpaste).

### 3.3.3 Study Period

The duration of the study is defined for each subject as the date that the signed electronic informed consent (eIC) is provided through the end of the study follow-up period (168 days [+7days] post-baseline), subject death, early withdrawal from the study, lost to follow-up or overall study termination.

## Statistical Analysis

## 4.1 Sample Size Calculation

No formal sample size calculation has been performed for this study however sufficient subjects will be screened (estimated screen failure 50%) to have approximately 650 subjects enrolled and 400 completers (estimated 40% drop-out).

There is no prior information for the use of DHEQ in DH sufferers in a RWE setting. It is believed that for this study 400 subjects are deemed sufficient to observe a trend over time from baseline at 24 weeks in total score.

PPD	GSK-001 SAP	
	Page 9 of 14	Version
	70114	1.0

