This study will aim to evaluate changes in oral health-related quality of life (OHrQoL) in subjects suffering from DH following the use of anti-sensitivity toothpaste for 24 weeks. Subjects' self-perception of DH will be evaluated by completion of a validated OHrQoL questionnaire (DHEQ-48) at baseline, 4, 8, 12, 16, 20 and 24 weeks.

Sufficient number of subjects (estimated 50% screen failure) aged between 18-65 years, who suffer from tooth sensitivity, will be screened to enroll approximately 650 to ensure 400 consumers complete the entire study (estimated 40%drop-out).

Subjects will be recruited through social media and other digital platforms. Subjects interested in the study will be sent to a landing page after clicking on an "Ad" or study link where they fill-out an initial pre-screening questionnaire and, if they are eligible, they will be sent an email with provided unique participant ID and the link to download the PPD app. After downloading the PPD app and logging in using a unique participant ID provided, they will review the electronic Inform Consent (eIC), they will be able to communicate with the PPD app's chat, via phone (study number linked to the study chat) or email. Subjects can use any or all of these methods as often as they need to until they are comfortable with their decision and may then accept or decline the eIC. No study-specific data collection will occur prior to subject consent. Subjects who do not actively access the study-specific website/app and provide consent will not have the possibility to contribute study data.

Once the subjects sign the eIC, they will complete a screening questionnaire which will aim to identify and exclude individuals whose sensitivity could be caused by other factors/clinical pathology for which dental healthcare professional advice should be sought. Subjects who qualify based on inclusion/exclusion criteria and the screening questionnaire will be enrolled and will be sent a desensitizing toothpaste (5% potassium nitrate). They will be asked to use it for 24 weeks, following the commercial tube instructions, recommended daily use and their normal oral healthcare habits, and to fill in the DHEQ form on 7 different occasions (Baseline (prior to any product use), 4, 8, 12, 16, 20 and 24 weeks).

At each DHEQ timepoint, subjects will receive reminders according to the schedule of activities.

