Safety will be assessed by evaluation of AEs and will be collected remotely via an online, subject portal.

Study Products:

Sensodyne Fresh Mint Toothpaste (potassium nitrate 5%, sodium fluoride 0.15% w/v fluoride ion — CC USA marketplace toothpaste)

Protocol Number: 216953

Type and Planned Number of Subjects:

Sufficient number of subjects will be screened (estimated 50% screen failure) to enroll approximately 650 to ensure 400 evaluable subjects complete the entire study (estimated 40% drop out).

Statistical Analyses

For the primary objective, plots of the mean values for questions Q1-3 (section1) and for questions in section 2 total DHEQ score (sum Q1-34), each of the domain's mean values: Restrictions (sum Q1-4), Adaptation (sum Q5-16), Social Impact (sum Q17-21), Emotional Impact (sum Q22-29), Identity (sum Q30-34), Global oral health (Q35) and Effect on life overall (sum Q36-39) will be presented for the overall population of DH sufferers over 24 weeks to assess QoL over time, graphically.

The analyses for exploratory objectives are defined in the statistical section 12.4.3.

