5 STUDY POPULATION

5.1 Type and Planned Number of Subjects

Sufficient number of subjects will be screened (estimated 50% failure rate) to enroll approximately 650 to ensure approximately 400 evaluable subjects complete the entire study (estimated 40% drop out).

An enrolled subject is one who has agreed to participate in the clinical study following completion of the informed consent process directly and successfully met eligibility criteria to proceed beyond screening as applicable for the protocol design.

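### Does enrolling about 650 with 40% drop-out fall short of the 400 completers the plan counts on?

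*SAP*

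**What the plan says.** Both documents give three planning numbers together: enrolment, drop-out and completers.

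- SAP 4.1 and Protocol 12.1: "approximately 650 subjects enrolled and 400 completers (estimated 40% drop-out". Both sections say that no formal sample size calculation was performed, that nothing is known beforehand about the DHEQ in a real-world setting, and that 400 is judged enough to see a trend in total score at 24 weeks.
- Protocol 1.1, study design paragraph (repeated in Protocol 4.1): "enroll approximately 650 to ensure 400 consumers complete the entire study".
- Protocol 1.1, planned number of subjects: "enroll approximately 650 to ensure 400 evaluable subjects complete the entire study (estimated 40% drop out".
- Protocol 5.1: "enroll approximately 650 to ensure approximately 400 evaluable subjects complete the entire study".
- SAP 3.3.1: "This will ensure approximately 400 evaluable subjects complete the entire study (estimated 40% drop out".

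The strength of the claim varies. Protocol 1.1 and 4.1 use *ensure* with an unqualified 400. Protocol 5.1 and SAP 3.3.1 use *ensure* but make the 400 approximate. Protocol 12.1 and SAP 4.1 state 400 completers without *ensure*. The 650 is approximate and the 40% is an estimate wherever they appear.

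**The concern.** Multiplying the first two numbers does not give the third: at the plan's own drop-out rate, 650 enrolled leaves 390. This is the only sample-size rationale in the trial, and 400 is the only number tied to what the study hopes to see. If the design does not deliver that number by its own assumptions, a reader may ask whether the rationale holds at all.

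A second worry sits beside the arithmetic. The 400 are called completers in some places and evaluable subjects in others, while efficacy is analysed in the mITT population, which needs only one dose and one post-baseline DHEQ-48. The number justified might therefore not be the number analysed. Finally, the claim that 400 is enough comes with no precision.

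**Working it through.** **Inputs.** Enrolment N ≈ 650, drop-out d ≈ 0.40, completers C = 400 (SAP 4.1, Protocol 12.1). The documents give no SD, effect size, alpha or power.

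**1. The plan's figure.** C = N × (1 − d) = 650 × 0.60 = 390. The stated 400 is 10 higher, and 10/400 = 2.5%. The common slip of inflating by (1 + d) would have given 400 × 1.40 = 560 enrolled, so the plan did not make that mistake.

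**2. What would make the three numbers agree exactly.**

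| Keep | Solve for | Result |
|---|---|---|
| N = 650, d = 40% | C = 650 × 0.60 | 390 |
| C = 400, d = 40% | N = 400 / 0.60 = 666.7 | 667 |
| N = 650, C = 400 | d = 1 − 400/650 | 38.5% |

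**3. Is this more than rounding?** A drop-out of 38.5% is 40% to the nearest five points. An enrolment of 667 is 650 to the nearest 50. Either reading lets all three published numbers stand as rounded values. The discrepancy is 2.5% on completers, or 17/650 = 2.6% on enrolment.

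**4. Against chance variation.** Assume that each subject completes independently with probability 0.60. The SD of the number of completers is then √(650 × 0.60 × 0.40) = √156 = 12.5. The shortfall of 10 is 10/12.5 = 0.8 SD, less than the spread expected even if the 40% were exactly right.

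**5. Effect on precision.** For any mean whose standard error scales with 1/√n, moving from 400 to 390 multiplies the half-width of the confidence interval by √(400/390) = 1.013. In SD units, the 95% half-width for a single week 24 mean is 1.96/√400 = 0.098 against 1.96/√390 = 0.099.

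The aim concerns change from baseline, so the more relevant quantity is a within-subject difference. With equal SDs and baseline-to-week-24 correlation r, its half-width is 1.96 × √(2(1 − r)) / √n. The documents give no r, so the values below are assumptions.

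| Assumed r | √(2(1 − r)) | Half-width, n = 400 | Half-width, n = 390 |
|---|---|---|---|
| 0.2 | 1.265 | 0.124 SD | 0.126 SD |
| 0.5 | 1.000 | 0.098 SD | 0.099 SD |
| 0.8 | 0.632 | 0.062 SD | 0.063 SD |

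The unknown correlation doubles or halves the precision, while the 10 subjects move it by 1.3%.

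**6. What the 400 feeds.** Protocol 12.4.1 and SAP 4.3.6 make the primary analysis plots of means. Protocol 12.2 and SAP 4.3.1 limit efficacy summaries to mITT. Protocol 12.4.4 says that no per-protocol analysis is planned. Protocol 12.4.7 and SAP 4.3.8 keep the available visits of subjects who miss others. No planned analysis is restricted to completers.

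**The case for a change.** The best case for a change rests on *ensure*, not on the 2.5%. An expected count of 390 does not ensure 400. Under the independence assumption in step 4, the chance of at least 400 completers is about 22% with 650 enrolled, and only about 52% with 667. The verb is unsupported at either enrolment. That stands. It also shows that the fault is in the wording: raising enrolment to 667 would not make the sentence true.

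The second argument is that *evaluable* and completer are not defined in either population section and are used as if they meant the same. Protocol section 8 lets subjects stay in after missing a DHEQ-48, so a subject can finish the study without week 24 data, and one who leaves after week 4 can still be in mITT. This is true, and the terminology is loose. But the analysis set itself is not in doubt, because both documents name mITT for efficacy. The 400 is a recruitment target, so asking the plan to say that mITT is the analysis set asks for text already there. For the same reason, relabelling 390 completers as 390 subjects with week 24 data would assume something the documents do not establish.

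The third argument is that the plan should state the precision it delivers, about 0.10 SD. A descriptive study can usefully do this. However, that figure is the precision of a single week 24 mean. It matches the change from baseline only if r = 0.5, as the table shows. Putting it in the plan would replace an openly declared judgement with a number for the wrong quantity.

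**Conclusion.** The concern does not call for a change. The arithmetic is right: 650 at 40% drop-out gives 390, which is 10 below 400. But the inputs are declared approximate or estimated, the gap is 2.5%, and no error rate, power statement or analysis set depends on it. Its effect on precision is a 1.3% wider interval. The unqualified *ensure* in Protocol 1.1 and 4.1 and the undefined *evaluable* are clerical slips, which any reader of the populations sections can resolve. They could be tidied if those sections are opened for another reason.

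This rests on two things: that the study stays descriptive with no formal hypothesis tied to 400, as both documents state, and that the standard error scales with 1/√n, so that a small change in n has a small effect. The 22% and 52% figures also assume independent completion at exactly 60%. The verdict does not depend on them.
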